9.6 Expansion Phase

As of June 2015, the recommended phase II dose of BYL719 has been determined to be 350mg for Arm D and we are currently enrolling 10 patients to the corresponding arm in the expansion phase of the study. The purpose of the expansion phase is to further define the safety and feasibility of BYL719 daily or intermittently in combination with letrozole or exemestane, and to estimate efficacy.

Patients will be eligible for only one of the four arms depending on which AI (letrozole or exemestane) they were taking immediately prior to study enrollment. Patients will not be randomized to one of the four arms.

In the expansion phase, BYL719 will be administered orally on the same administration schedule for that arm as for the dose-finding phase and at the dose established in the dose-finding phase of the trial. For Arm D, the established dose is 350mg for BYL719. Patients will continue on treatment until progression of disease or unacceptable toxicity.

In order to help ensure that the DLT rate observed among the additional 10 patients in each arm is consistent with the DLT rate observed at the established dose from the dose-finding portion, the following decision rule will be implemented for each of the two study arms. If ≥ 4 DLTs are seen at any time in any one expansion arm, then it is likely that the safe and tolerable dose determined during the dose-finding portion of the trial is too toxic. The safety data will then be reviewed with the primary investigator and Novartis to determine how to move forward. Depending on the circumstances, we may consider de-escalating the dose of BYL719 to the next lower dose level and accruing 10 additional patients at that level. The probability of observing at least 4 patients with a DLT in the 10 additional patients is .28 if 1 of 6 patients were seen with a DLT in the dose-finding phase of the study. The probability of observing at least 4 patients with a DLT in the 10 additional patients is .09 if 0 of 6 patients were seen with a DLT in the dose-finding phase of the study.¹¹

The two arms of the study will be monitored in tandem, and we have added an overall sequential global stopping rule to be applied as both expansion cohorts are accruing. We include this early stopping rule across both arms because the mechanism and toxicities of both AIs are known to be very similar. Our global stopping rule is based on repeated significance testing and serves as a global safety measure. We assume a grade 4 toxicity rate of 10% as acceptable and 35% as unacceptable. With these assumptions, if 2 of the first 5 patients, 3 of the first 10 patients, 4 of the first fifteen or 5 of 20 patients accrued experience a grade 4 toxicity, we will discontinue the entire study. With this rule, the probability of discontinuing the study if the true toxicity rate is 35% is .92. If the true toxicity rate is 10%, this probability is .10.

Likewise, if two different recommended phase II doses are determined in the separate arms, safety data will be reviewed with the primary investigator and Novartis, and we will determine how to move forward. Depending on the circumstances, we will consider reducing the dose of BYL719 in the unaffected arm of the trial, if felt to be appropriate to ensure patient safety.

9.7 Concomitant Medications

All medications (other than the study drugs) taken within 4 weeks of study treatment initiation and all concomitant therapy and significant non-drug therapies (including physical therapy and blood transfusions) administered during the study, with reasons for use, should be recorded. Medications include not only physician prescribed medications, but also all over-the-counter medications, herbal medications and nutritional or vitamin supplements.

The investigator should instruct the patient to notify the study site about any new medications he/she takes after starting study drug. Upon enrollment, patients should be given the handout titled "Patient Information for BYL719 Drug and Food Interactions" (Appendix C), and this information should be reviewed with the patient.

Patients taking medication chronically should be maintained on the same dose and schedule throughout the study period, as medically feasible. The days of full pharmacokinetic blood sampling should be representative of the other study days with regard to the use of the chronically administered concomitant medications. However, if a concomitant medication is used intermittently during the study, this medication should be avoided on the days of full pharmacokinetic sampling, if medically feasible.

9.6.1 Permitted concomitant therapy

In general, the use of any concomitant medication/therapies deemed necessary for the care of the patient is permitted, except as specifically prohibited in Section 9.6.3.

Antiemetics: Use of anti-emetics is allowed. Prophylactic anti-emetics should be started only once the patient experienced nausea or vomiting at the discretion of the investigator (refer to Table 10-2 for toxicity management guidelines). It is recommended that patients use drugs that do not cause QT prolongation. Please note that some anti-emetics have a known risk for Torsades de Pointes (e.g., chlorpromazine, droperidol, haloperidol) and are prohibited (refer to Section 9.6.3 and Appendix F). Some other anti-emetics (e.g., ondansetron) are to be used with caution (refer to Appendix G).

Bisphosphonates: The use of bisphosphonates regardless of indication is allowed provided patients have been on stable doses for at least 2 weeks prior to study entry. Stable dose should be maintained during the treatment period. Patients requiring initiation of bisphosphonates during the course of the study should be discontinued due to progressive disease unless disease progression can be completely ruled out and this is clearly documented in the patients' source documentation.

Oral anti-diabetics: Patients who develop diabetes mellitus during the study should be treated according to the ADA (American Diabetes Association) guidance (refer to Section 10.10.3). Patients receiving oral antidiabetics which are predominantly metabolized by CYP2C9 and CYP2C8, including but not limited to, repaglinide, rosiglitazone, glipizide and tolbutamide, must be carefully monitored for hypoglycemia as BYL719 was found to be moderate reversible inhibitor of these enzymes (refer to Appendix D).

9.6.2 Permitted concomitant therapy requiring caution and/or action

Hematopoietic growth factors: Hematopoietic growth factors (e.g. erythropoietins, G-colony stimulating factor (CSF) and GM-CSF) are not to be administered prophylactically. Use of these drugs should be reserved to patients with severe neutropenia and anemia as per the labeling of these agents or as dictated by local practice (see also the guidelines established by the American Society of Clinical Oncology).

Anticoagulation: Anticoagulants other than warfarin/coumarin derivatives or antiaggregation agents may be administered under the discretion of the investigator (refer to Section 9.6.3). However, caution is advised when BYL719 is co-administered with anti-platelet pro-drugs such as clopidogrel, ticlopidine and prasugrel, which require metabolic activation by CYP3A4, CYP2C9 and CYP2C19. BYL719 has the potential to inhibit these enzymes and may therefore decrease the metabolic activation and clinical efficacy of these pro-drugs. Patients using anti-platelet pro-drugs should be carefully monitored.

CYP450 substrates: In vitro studies demonstrate that BYL719 is a mechanism based inhibitor of CYP3A4. BYL719 may increase exposure to drugs metabolized by CYP3A4 by more than 5-fold. BYL719 may also inhibit the metabolic clearance of co-medications metabolized by CYP2C8, CYP2C9, CYP2C19, if sufficiently high BYL719 concentrations are achieved in vivo. Investigators, at their discretion, may administer concomitant medications known to be metabolized by CYP3A4/5, CYP2C8, CYP2C9 and CYP2C19 (refer to Appendix D). Patients receiving such medications must be carefully monitored for potential toxicity due to any individual concomitant medications. Particularly, caution is advised when BYL719 is co-administered with drugs that are sensitive substrates for CYP3A4, CYP2C8, CYP2C9 or CYP2C19 and which have a narrow therapeutic index (Appendix D, footnote 2).

Opioid analgesics: Caution is advised when BYL719 is co-administered with opioid analgesics. Inhibition of opioid metabolism by CYP3A4 can lead to opioid toxicity, including fatal respiratory depression, or an enhanced risk for QTc prolongation. Patients receiving BYL719 and opioid analgesics should be carefully monitored. Synthetic opioids with clinically relevant interactions with CYP3A4 inhibitors include, but are not limited to, propoxyphene, fentanyl, alfentanil and sufentanil. Use of alfentanil, a sensitive CYP3A4 substrate with narrow therapeutic window, should be fully avoided whenever possible. The use of methadone or levomethadyl is prohibited (refer to Appendix F).

Drugs with a conditional or possible risk to induce Torsade de Pointes (TdP): Please refer to Section 9.3.3 and Appendix F for a list of prohibited QT prolonging medication. If a patient, enrolled in the study, requires the concomitant use of any medication with a possible or conditional risk for TdP (see Appendix G for a list of such medications), then investigators, at their discretion, may co-administer such medications. Patients receiving such medications must however be monitored.

Gastric protection agents: BYL719 is characterized by a pH-dependent solubility. Medicinal products that alter the pH of the upper gastro-intestinal tract may alter the solubility of BYL719 and hence its bioavailability. These agents include, but are not limited to, proton-pump inhibitors (e.g., omeprazole), H₂-antagonists (e.g., ranitidine) and antacids. BYL719 should preferably be dosed in a staggered manner, i.e., at least 1 hour before or 10 hours after dosing with a gastric protection agent. Note that some proton pump inhibitors may possibly inhibit BCRP (refer to Appendix E). The treatment with BCRP inhibitors should be kept as short as possible or, if possible, fully avoided.

BCRP Inhibitors: BYL719 was identified as a substrate for the human BCRP. Co-administration of BYL719 with BCRP inhibitors may possibly increase systemic exposure

and/or alter tissue uptake of oral BYL719. The treatment with BCRP inhibitors should be kept as short as possible or, if possible, fully avoided. See Appendix E for a list of BCRP inhibitors.

Palliative radiotherapy: Local radiotherapy for analgesic purposes or for lytic lesions at risk of fracture may be carried out if required. Whenever possible, these patients should have a tumor assessment of the lesion(s) before they actually receive the radiotherapy in order to rule out progression of disease. In case of disease progression, patients should discontinue treatment and be removed from the study. No dose modification of study treatment is needed during radiotherapy.

Steroids: Chronic administration of corticosteroids (> 5 days) can induce CYP3A4. Due to this and concern for hyperglycemia, steroids should be used briefly and with caution. Patients who have a current need for chronic corticosteroid therapy at the time of screening (≥ 10 mg of prednisone daily or an equivalent dose of other corticosteroid) are not eligible to enroll.

9.6.3 Prohibited concomitant therapy

Other investigational and antineoplastic therapies: Other investigational therapies must not be used while the patient is on the study. Systemic anticancer therapy (chemotherapy, biologic) other than the study treatments must not be given to patients while the patient is on the study medication. If such agents are required for a patient then the patient must be discontinued from the study.

Drugs with a known risk for Torsades de Pointes (TdP): If a patient, enrolled in the study, requires the concomitant use of any medication included in Appendix F entitled "List of Prohibited QT prolonging drugs" (i.e., drugs that are generally accepted by the Qtdrugs.org Advisory Board of the Arizona CERT to have a known risk of causing TdP), BYL719 administration must be interrupted as long as the patient requires therapy with the QT prolonging agent. Note that Appendix D also includes drugs that are substrates for CYP3A and CYP2C with a possible or conditional risk for TdP. If the patient requires long term therapy with such a QT prolonging agent, leading to study treatment interruption of > 21 days, the patient must be permanently discontinued from BYL719.

Herbal medications: Herbal preparations/medications are not allowed throughout the study. These herbal medications include, but are not limited to: St. John's wort, Kava, ephedra (ma huang), ginkgo biloba, dehydroepiandrosterone (DHEA), yohimbe, saw palmetto, and ginseng. Patients should stop using these herbal medications 7 days prior to first dose of study drug.

Warfarin and coumarin derivatives: Therapeutic doses of warfarin sodium (Coumadin®) or any other coumarin-derivative anticoagulants are not permitted. Warfarin has a narrow therapeutic range and BYL719 is a possible inhibitor of CYP2C8 and 2C9, the major metabolizing enzyme of warfarin. Therapeutic anticoagulation may be accomplished using low-molecular weight heparin.

Opioid analgesics: See Section 9.3.2 for opioid analgesics to be used with caution. Use of alfentanil, a sensitive CYP3A4 substrate with narrow therapeutic window, should be fully avoided whenever possible. The use of methadone or levomethadyl is prohibited.

10.0 EVALUATION DURING TREATMENT/INTERVENTION

10.1 Evaluation Summary

Table 10-1 Evaluation Summary Chart

	Pre- Rx ^a	Cycle 1 Day 1	Cycle 1 Day 8 (+/- 3 days)	Cycle 1 Day 15 (+/- 3 days)	Cycle 2 Day 1 (+/- 3 days)	Cycle 2 Day 15 (+/- 3 days)	Cycle 3+ Day 1 (+/- 7 days) ^h	End of Rx (within 28 days) ^b
Letrozole or Exemestane	Continuous daily dosing, Days 1-28							
BYL719, Arm A/B	Continuous daily dosing, Days 1-28							
BYL719, Arm C	Days 1-7, 15-21 of 28 day cycle							
BYL719, Arm D	Days 1-5, 8-12, 15-19, 22-26 of 28 day cycle							
Tumor biopsy	X			X				X
History and physical	X	X	X	X	X	X	X	X
Toxicity assessment		X	X	X	X	X	X	X
Assessment of Concomitant Medications	X	X	X	X	X	X	X	X
Complete blood count (CBC)	X	X		X	X	X	X	X
Comprehensive metabolic panel (CMP)	X	X		X	X	X	X	X
Magnesium, amylase, lipase	X	X		X	X	X	X	X
PT/INR and PTT	X							
Fasting glucose	X	X		X	X	X	X	X
Tumor markers (CA15-3 and CEA)		X			X		X	X
Blood draw for companion normal DNA ^c	X							
Blood draw for plasma collection (cfDNA)	X	X	X	X	X		X	X
EKG ^j	X	X		X	X	X	X ^u	X
EOD evaluation ⁿ	X						X ^u	X ^e
Research PK		X		X	X	X	X ^r	
Estradiol ^s	X						X ^d	
	^a See Section 8 for required time frames for pre-treatment studies ^b Pre-treatment and Day 15 on-treatment biopsies will be required, unless felt to put the patient at unacceptable risk (note: patients with bone-only metastases will have a pre-treatment biopsy only). See Section 10.12 for processing. The tumor biopsy is not required to be scheduled on the same day as the MD visit. While every attempt will be made to schedule the on-treatment tumor biopsy on Day 15, the exact timing of the research biopsy will be at the discretion of the investigators. All patients may be asked to undergo an optional tumor biopsy at progression, with the exact timing to be at the discretion of the investigator and patient (not necessarily within 28							

	
days of last dose of BYL719), although a 2 week window is allowed.
 
c Companion normal DNA for targeted gene sequencing analysis (1ml whole blood for correlative science, Section 10.12)
 
d Day 1 +/- 7 days of Cycle 3, Cycle 5, and then every 3rd cycle (Cycle 8, Cycle 11, etc)
 
e If EOD not already performed in the last 28 days
 
f Cycle 3, Cycle 4, Cycle 5, Cycle 6, Cycle 8 and Cycle 10 for letrozole arm (Arm A) and Cycle 3 only for exemestane arm (Arm B)
 
g Estradiol to be tested only on women who are receiving pharmacologic ovarian suppression
 
h Patients on study under Amendment 13 will have relevant blood and cfDNA collection every other cycle (+/- 7 days).
 
i Patients on study under Amendment 13 will have EOD evaluations will be preformed every 16 weeks +/- 4 weeks from their last scan.
 
j Patients on study under Amendment 13 will have EKG evaluations every 4 cycles. EKG evaluations may be preformed more frequently at the discretion of the MD.

--	---

10.2 Cycle 1 Day 1

- 10.2.1 MD visit, with history and physical examination, including weight, blood pressure, pulse, ECOG performance status, and updated medication list. Concurrent medications will be reviewed for potential drug-drug interactions with study medication (see Section 9.6).
- 10.2.2 Toxicity will be assessed and the type, severity, timing, and relationship of each adverse event to therapy will be determined as per the NCI Common Toxicity Criteria, version 4.0.
- 10.2.3 Fasting bloodwork prior to taking BYL719 in clinic on this day (if screening bloodwork was not performed within 72 hours of dosing). A light breakfast may be consumed after fasting plasma glucose draw. BYL719 may be administered 1 hour after breakfast. Patients should fast for 1 hour after the administration of BYL719. Bloodwork results do not need to be resulted prior to dosing on this day; however, all bloodwork must be reviewed and the patient contacted within 24 hours (excluding weekends and holidays) if an abnormality is detected which would affect dosing. If a patient is being screened and starting treatment on the same day, then results of CBC, CMP and fasting glucose must be reviewed prior to enrollment and initiation of treatment.
- CBC, including WBC (differential not required), Hgb and platelet count
 - CMP, including BUN, creatinine and liver function tests
 - Magnesium, amylase and lipase
 - Fasting glucose
 - PT/INR and PTT
 - Tumor markers (CA 15-3 and CEA)
 - Plasma collection from 10 ml blood for cfDNA extraction analysis
- 10.2.4 EKG will be performed (if screening EKG was not performed within 72 hours of dosing). EKG must be reviewed prior to dosing.

10.2.5 PK bloodwork for research purposes (see schedule in Section 10.11).

10.2.6 Patients will be prescribed or advised to take an over the counter antihistamine daily, unless contraindicated for that specific patient. Initiation of anti-histamine therapy is recommended but not required at the start of BYL719 therapy.

10.3 Cycle 1 Day 8 (+/- 3 days)

10.3.1 MD visit, with history and physical examination, including weight, blood pressure, pulse, ECOG performance status, and updated medication list. Concurrent medications will be reviewed for potential drug-drug interactions with study medication (see Section 9.6).

10.3.2 Research blood draw for plasma collection from 10ml blood for cfDNA extraction and analysis

10.4 Cycle 1 Day 15 (+/- 3 days)

10.4.1 MD visit, with history and physical examination, including weight, blood pressure, pulse, ECOG performance status, and patient drug diary review.

10.4.2 Toxicity will be assessed and the type, severity, timing, and relationship of each adverse event to therapy will be determined as per the NCI Common Toxicity Criteria, version 4.0.

10.4.3 Fasting bloodwork prior to taking BYL719 in clinic on this day. A light breakfast may be consumed after fasting plasma glucose draw. BYL719 may be administered 1 hour after breakfast. Patients should fast for 1 hour after the administration of BYL719. Bloodwork results do not need to be resulted prior to dosing on this day (because BYL719 dosing is continuous); however, all bloodwork must be reviewed and the patient contacted within 24 hours (excluding weekends and holidays) if an abnormality is detected which would affect dosing.

- CBC, including WBC (differential not required), Hgb and platelet count
- CMP, including BUN, creatinine and liver function tests
- Magnesium, amylase and lipase
- Fasting glucose
- Plasma collection from 10 ml blood for cfDNA extraction and analysis

10.4.4 EKG will be performed and reviewed prior to dosing.

10.4.5 PK bloodwork for research purposes (see schedule in Section 10.11).

10.4.6 Day 15 on-treatment tumor biopsy will be required, unless felt to put the patient at unacceptable risk (note: patients with bone-only metastases will have a pre-treatment biopsy only). This biopsy is for research purposes. After obtaining separate informed consent, a core biopsy will be obtained and processed for proteomic analysis (Section 10.12). The tumor biopsy should be taken 2-8 hours after the BYL719 dose on that day. The tumor biopsy is not required to be scheduled on the same day as

the MD visit. While every attempt will be made to schedule the tumor biopsy on Day 15, the exact timing of the research biopsy will be at the discretion of the investigators.

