9.1 TREATMENT/INTERVENTION PLAN

9.2 Aromatase Inhibitor Administration

This clinical trial was initially comprised of two arms, one for BYL719 in combination with letrozole (Arm A), and another for BYL719 in combination with exemestane (Arm B). As of January 2014, the study is being amended to include two additional arms, and patients will no longer be enrolled onto Arms A or B. On Arm C, patients will receive intermittent BYL719 (7 days on, 7 days off) in combination with daily letrozole, and on Arm D, patients will receive intermittent BYL719 (5 days on, 2 days off) in combination with daily exemestane. Patients will be eligible for only one of the two arms, Arm C or Arm D, depending on which AI

(letrozole or exemestane) they were taking before study enrollment (i.e., a patient who was taking letrozole will continue to take letrozole, and a patient who was taking exemestane will continue to take exemestane). Patients will not be randomized to one of the two arms.

Letrozole or exemestane will be self-administered by the study patients orally once daily. . On days that patients are taking BYL719, aromatase inhibitor should be swallowed concomitantly with BYL719, or less than 5 minutes apart, at approximately the same time every day. The recommended time of administration is approximately 9 am (+/- 2 hrs). On a day of PK bloodwork, patients will take the scheduled dose in clinic. Treatment doses for each AI will be fixed at the established dose (see Table 9-1 below). There will be no dose escalation or dose reduction for letrozole or exemestane.

Table 9-1

Arm	AI dose	BYL719 schedule (dose per cohort)
A	Letrozole 2.5mg orally once daily	Days 1-28 of 28 day cycle
B	Exemestane 25mg orally once daily	Days 1-28 of 28 day cycle
C	Letrozole 2.5mg orally once daily	Days 1-7, 15-21 of 28 day cycle
D	Exemestane 25mg orally once daily	Days 1-5, 8-12, 15-19, 22-26 of 28 day cycle

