14.5 Exploratory Objectives

Correlative studies examining patient and clinical factors correlated with BYL719 sensitivity will be done using next generation sequencing and fine copy number analysis of pre-treatment biopsies, as well as proteomic analysis of pre-treatment and on-treatment biopsies. cfDNA analysis in plasma obtained at baseline, Cycle 1 day 1, Cycle 1 day 8, Cycle 1 day 15 and at each subsequent treatment cycle will be performed to assess for a correlation between mutant allele quantification and response to BYL719. We feel that combining the letrozole and exemestane arms for these exploratory analyses is reasonable given their similar mechanisms of action at the level of the breast cancer cell. The correlative studies will be primarily descriptive and provide the preliminary evidence necessary to recommend BYL719 and specific biomarkers for future clinical study.

cfDNA extraction from 2-6 ml plasma obtained at the time of routine blood draws has been feasible in patients with metastatic breast cancer according to ongoing study, MSKCC IRB #13-050, [name] – PI. DNA quantity and integrity is assessed by qPCR and uniformly has yielded amplifiable fragments suitable for dPCR and small amplicon library construction. We anticipate that this approach will be informative for patients with tumors harboring a *PIK3CA* mutation and exploratory for patients whose tumors harbor potential driver mutations for which additional dPCR assays will be designed ([Dawson, Tsui et al. 2013](#)).

The protocol consent form asks participants for permission to discuss their research findings if their samples are used in an HBUC or Biospecimen project and an incidental finding is made that may be critical to their preventative care. If a participant agrees to be contacted, the participant will not be told the specific results of the research test, but will be informed that their samples were used in a project and a potential risk was uncovered. If the participant is interested in further discussion of the research findings, the participant will be

asked to come into MSKCC Clinical Genetics Service for counseling and specific genetic testing.

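### The Day 15 biopsy section was not adapted to intermittent dosing, and the marker correlation in Section 14.5 takes no account of schedule

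*Combined protocol and SAP*

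**What the plan says.** Table 9-1 (Section 9.2) and Table 10-1 give the BYL719 calendars. Arms A and B: "Days 1-28 of 28 day cycle". Arm C: "Days 1-7, 15-21 of 28 day cycle". Arm D: "Days 1-5, 8-12, 15-19, 22-26 of 28 day cycle".

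Section 10.4 covers the Cycle 1 Day 15 visit, which has a window of 3 days either side, and Table 10-1 lists the biopsy under that visit. On timing relative to the dose, Section 10.4.6 states: "The tumor biopsy should be taken 2-8 hours after the BYL719 dose on that day". It asks the team to aim for Day 15, lets the biopsy fall on a different day from the clinic visit, and adds that "the exact timing of the research biopsy will be at the discretion of the investigators". Section 10.4.3, on the same visit, explains why laboratory results may wait with the words "because BYL719 dosing is continuous".

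Section 2.3 lists Arms A, B, C and D under a single pharmacodynamic objective. Section 14.5 says: "We feel that combining the letrozole and exemestane arms for these exploratory analyses is reasonable". Its reason is that the two aromatase inhibitors act alike on the tumor cell. It then plans one Spearman correlation between the within-patient change in the pathway signature and the change in tumor volume at the 8-week CT. BYL719 schedule is not mentioned.

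**The concern.** The biopsy is meant to show how far the pathway is inhibited on treatment. After a planned break it shows the response to a newly restarted drug; in the continuous arms it shows the response after two weeks of daily doses. These are not the same measurement, and the plan does not say so.

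The other side of the correlation also depends on schedule, because the arms receive different amounts of drug before the 8-week CT. A factor that acts on both variables can produce a pooled association that reflects the arm, or mask one that exists within arms. The reason given for combining concerns the aromatase inhibitors only. In Arms C and D the two are inseparable: every letrozole patient is on the 7-on/7-off schedule and every exemestane patient on 5-on/2-off, so combining the inhibitors also combines the schedules.

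At stake is how an exploratory result is read. Section 14.5 would take the correlation as evidence that the markers predict response, and would use the correlative work to recommend biomarkers for later study.

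**Working it through.** **The plan's own figure.** Section 14.5 expects Day 15 biopsies in at least 50% of 38 patients: 0.50 × 38 = 19, as stated. Section 14.1 gives 38 as the anticipated total for Arms C and D.

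**Calendar.** The visit window is Days 12-18. Comparing it with Table 9-1:

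| | Arms A/B | Arm C | Arm D |
|---|---|---|---|
| Dosing days in window | 12-18 | 15-18 | 12, 15-18 |
| Off-days in window | none | 12-14 | 13-14 |
| Last dose before Day 15 | Day 14 | Day 7 | Day 12 |
| Gap to Day 15 dose | 24 h | 8 × 24 = 192 h | 3 × 24 = 72 h |
| Consecutive dose number on Day 15 | 15 | 1 | 1 |
| Planned dosing days in two cycles | 2 × 28 = 56 | 2 × 14 = 28 | 2 × 20 = 40 |

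**Drug left from the earlier block.** Share remaining = 0.5^(gap / half-life). Section 3.5.2 gives a half-life of about 10 h.

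- A/B: 0.5^2.4 = 19%
- C: 0.5^19.2 = 0.0002%
- D: 0.5^7.2 = 0.7%

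If the half-life were 20 h (an assumption), the shares would be 44%, 0.13% and 8.2%. At either value, Arm C starts afresh on Day 15 and Arm D nearly so.

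**Exposure when the biopsy is taken.** Residual drug before the dose is a trough quantity, whereas the biopsy comes 2-8 h after a dose. The relevant comparison is exposure on the k-th consecutive dose as a share of steady state, 1 − 0.5^(24k/10) in a one-compartment model:

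- k = 1 (Day 15, Arms C and D): 1 − 0.5^2.4 = 81%
- k = 2 (Day 16): 1 − 0.5^4.8 = 96%
- k = 5 (Day 12, Arm D): over 99%
- k = 15 (Day 15, Arms A/B): effectively 100%

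The shortfall on Day 15 is therefore about 19%.

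**Sensitivity.** Section 3.5.2 also reports roughly 3-fold accumulation at 400 mg daily (range 1.91 to 4.42). If that applied, a fresh first dose would give 1/3 = 33% of steady state, with a range of 1/4.42 = 23% to 1/1.91 = 52%. Whether it applies at the 200-350 mg levels of Arms C and D by Day 15 is an assumption. If such accumulation came from slower elimination, some drug would also survive the 2-day break: with a 40 h half-life, 0.5^(72/40) = 29% in Arm D and 0.5^(192/40) = 3.6% in Arm C. Arms C and D would then differ in exposure at biopsy as well.

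**Precision if split by schedule.** Nineteen biopsies divided evenly give 9 and 10. The Fisher approximation gives a 95% half-width of 1.96/√(n − 3) on the transformed scale.

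- Pooled, n = 19: 1.96/√16 = 0.49
- n = 9 alone: 1.96/√6 = 0.80
- n = 10 alone: 1.96/√7 = 0.74
- Two strata combined: 1.96/√(6 + 7) = 0.54

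Separate coefficients are imprecise, but a combined stratified estimate loses little against the pooled one.

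**The case against.** A reader might infer that the plan places the biopsy on an off-day in Arms C and D. It does not. Day 15 is a scheduled dosing day in every arm, the team is told to aim for it, and an instruction tied to that day's dose presupposes a dose. An off-day biopsy arises only if the date is moved earlier under the window or the investigators' discretion, against that instruction. What stands is that the passages conflict on those days.

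A reader might also infer that Arms C and D are to be pooled with steady-state biopsies from Arms A and B. Section 14.5 does not say so, and its expected 19 biopsies rest on the 38 patients of Arms C and D. Section 2.3 names all four arms, so such pooling is implied but not stated. Nor do the documents describe Arms A and B as at steady state: Section 3.7 places rash on continuous dosing at about Days 10-14 and says that it interrupts treatment, so some of those patients may have been off drug near Day 15. The point does not depend on Arms A and B, because Arms C and D alone combine breaks of 7 and 2 days, and 28 and 40 dosing days before the CT.

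The near-zero residuals overstate the difference. Median time to peak is 1.5 to 7.1 h (Section 3.5.2), so a biopsy at 2-8 h still captures acute inhibition. Above 180 mg, clearance in the first week agreed closely with single-dose clearance, and rising exposure was seen only after a month at 270 and 400 mg. That favors the 19% shortfall over the two-thirds shortfall.

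Finally, the analysis is descriptive, the strata are small, and accrual closed at 51 patients (Section 1.0). A new biopsy window can no longer change this trial's data. All of this stands, and it limits the fix to the analysis.

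**Conclusion.** The point holds as a minor one. Section 10.4 was carried over from continuous dosing: its rationale is wrong for Arms C and D, and its post-dose instruction cannot be met on three days of the window in Arm C and two in Arm D. On nominal Day 15 the intermittent arms are biopsied at about 81% of steady-state exposure, given a 10 h half-life and a one-compartment model. The one-third figure needs accumulation of the size seen at 400 mg, which is not established for these arms.

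At a 10 h half-life, Arms C and D have nearly equal exposure after the Day 15 dose. The difference between them lies in the length of the preceding break and the dosing before the CT; the contrast in exposure at biopsy is mainly with Arms A and B, if those are included.

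The documents do not show that any biopsy was taken on an off-day, or that the correlation would be distorted by a known amount. They show that schedule can affect both variables and that the planned analysis ignores it. No primary endpoint, sample size or stated error rate changes.

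**What to change.** In Section 14.5, state which arms enter the marker analysis. Compute the correlation of pathway change with tumor change within schedule (A/B, C, D), or with schedule as a stratum, and show it before any pooled estimate.

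From the dosing records and patient diaries that Section 9.3 already requires, together with the biopsy time, derive dose-to-biopsy time and consecutive dosing day for each biopsy. List these with the results and flag any biopsy taken on an off-day or during an interruption.

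For any reuse of the protocol, reconcile the Section 10.4 wording on continuous dosing, the visit window and the post-dose instruction with the Arm C and Arm D calendars.

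The cost is a few lines of text, retrieval of data largely in hand, and less precision: about 9-10 biopsies each in Arms C and D if the expected 19 split evenly. No extra biopsy or patient is needed.
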